9.2.2. Overall Summary of Adverse Events

An overall summary of crude AE incidences will be presented according to [Table 7](#), including the number and percent of subjects with at least one of:

- Any TEAE
- TEAE by maximum CTCAE Grade
- CTCAE Grade ≥ 3 TEAE
- Serious TEAE
- Fatal TEAEs (outcome="Fatal" or severity=CTCAE Grade 5)
- Treatment-related TEAE
- Treatment-related serious TEAE
- Treatment-related TEAE of CTCAE \geq Grade 3
- TEAE leading to infusion interruption

- TEAE leading to dose reduction
- TEAE leading to dose being held
- TEAE leading to prolongation of infusion time (>2.5 hours)
- Infusion associated TEAE as determined by the Investigator
- TEAE leading to study drug withdrawal

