5.3 DOSAGE, PREPARATION, AND ADMINISTRATION

Study drug consists of NEOD001. The NEOD001 dose is 24 mg/kg; however, the maximum dose administered is not to exceed 2500 mg. Therefore, subjects with a weight of 104.2 kg or greater will receive the maximum dose of 2500 mg. The subject's weight during Screening may be used for calculation of the first dose. Subsequent doses may be calculated based on the current weight at that visit or using the baseline weight, based on the site's institutional guidelines. A change of $\pm 10\%$ from the weight being used for dosing should trigger recalculation of the dose based on the new weight unless thought to be exclusively due to fluid fluctuation (e.g., edema).

Each vial of 500 mg of NEOD001 will be reconstituted with 9.6 mL sterile WFI to a concentration of 50 mg/mL resulting in a buffered, isotonic, preservative-free solution with a total extractable volume of 10 mL. Study drug will be prepared in a 250-mL IV bag of 0.9% saline. The equivalent volume of reconstituted NEOD001 will be withdrawn prior to transferring the drug solution into the IV bag, such that the total IV bag volume will be 250 mL.

Refer to the Pharmacy Manual for complete information on preparing and administering the study drug.

The study drug should only be administered in settings where emergency resuscitative equipment and personnel trained in the management of anaphylaxis are immediately available to treat systemic reactions under the direct supervision of a physician.

The study drug will be administered once every 28 (± 5) days at the infusion duration established in Study NEOD001-001 or over 60 (± 10) minutes. The length of the infusion may be extended over a longer period of time as clinically indicated.

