5.4.2 Management of Suspected Infusion-Related/Hypersensitivity Adverse Events

In the event of a suspected infusion-related and/or hypersensitivity AE, the infusion should be immediately discontinued and appropriate supportive therapy should be administered, which may include epinephrine, IV fluids, corticosteroids, vasopressors, oxygen, bronchodilators, antihistamines, or acetaminophen. Subjects should be evaluated and carefully monitored until there is complete resolution of the AE or hypersensitivity signs and symptoms. In addition to the institution's recommended assessments, blood samples should be obtained in the event of a suspected infusion-related and/or hypersensitivity AE for assessment of the following: tryptase, complements C3 and C4, serum NEOD001, and anti-NEOD001 antibody levels.

For subjects who have an infusion-related reaction, any subsequent infusion must be given with premedication. Within the 30-60 minutes before the start of each infusion, administer 25 mg diphenhydramine (or an equivalent H1 antihistamine) and 650 mg acetaminophen. All premedications will be recorded in the electronic case report forms (eCRFs).

For subjects with a Grade 2 infusion-related AE, if it is appropriate to restart the infusion, it should be done at 50% of the original rate (e.g., if the initial infusion is administered over 60 minutes, the new rate should be based on administering 250 mL over at least 90 minutes). If the subject is to receive additional infusions in subsequent weeks, the rate of these infusions should be discussed with and agreed upon prospectively by the Investigator and the Medical Monitor.

If a subject experiences a Grade 3 infusion-related and/or hypersensitivity AE, the infusion should not be restarted. The decision to continue dosing at the subject's next scheduled administration should be discussed with the Medical Monitor. If the decision is made to proceed with dosing, the dose will be reduced by 50%, in addition to a 50% reduction of the original infusion rate. Subjects who have an infusion-related and/or hypersensitivity AE at the subsequent scheduled study drug administration must have study drug permanently discontinued and have an EOS Visit per Section [6.1.3](#).

Subjects who experience a Grade 4 infusion-related and/or hypersensitivity AE must have study drug permanently discontinued and have an EOS Visit per Section [6.1.3](#).

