9.1. Extent of Exposure

Study drug exposure during the OLE and separately for the original parent study (NEOD001-001) and OLE combined will be summarized including:

- Total Number of Infusions received will be determined for each subject by number of times the start time of drug infused is reported. If multiple infusion start times are reported on a single day, then only 1 infusion will be counted for that day. If the start time of drug infused is missing but total volume infused is greater than 0 mL, 1 infusion will be counted for that day.
- Total Number of Dose Interruptions will be determined for each subject by the number of times the IV was not completed in OLE, or segment outcome of the infusion was interrupted in parent study.
- Dose Strength (mg/kg) will be calculated for each subject at each OLE visit and each visit in parent study separately as follows:
 - For each OLE visit, dose (mg) recorded on the Study Drug Exposure CRF will be divided by the weight (kg) at that visit (Vital Signs CRF). If the dose (mg) is missing but the total duration of infusion is at least 50 minutes which is the lower limit of the protocol specified time (i.e. 60 min – 10 min), and IV completed is marked “Yes” then dose strength will be imputed to be equal to the planned dose strength (described below).
 - For each visit in parent study, the total dose (mg) reported will be divided by the weight used to calculate dose strength for that visit. If Current Visit is marked for Weight Used to determine dose and no corresponding weight is available from the vital sign page then the screening/baseline weight will be assigned as the weight used to calculate total dose. Dose strength will only be calculated where both the total dose and weight used are available.

Once visit/individual specific dose strengths are determined, subjects will be assigned a single average dose strength value across all visits to be used for summary statistics in the table.

- Percent of Planned Dose Strength will be determined by dividing the average dose strength per visit by the average planned dose strength per visit for each subject. Calculation of average dose strength is described above. Planned dose strength will be assigned by visit based on NEOD001 dose level. The average of planned dose strength will be the average of the individual planned dose strength calculated at each visit.

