9.2.6. Adverse Events Leading to Dosing Changes

The crude and cumulative incidences of TEAEs leading to dosing changes will be summarized. The following summaries will be presented:

- Subject incidence of TEAEs leading to infusion interruption by MedDRA SOC and PT. This is a subset of the AEs where Action Taken with Study Treatment is checked as “Dose Interrupted” is checked.

- Subject incidence of TEAEs leading to dose reduction by MedDRA SOC and PT. This is a subset of the AEs where Action Taken with Study Treatment is checked as “Dose Reduced” is checked.
- Subject incidence of TEAEs leading to dose held by MedDRA SOC and PT. This is a subset of the AEs where Action Taken with Study Treatment is checked as “Dose Held” is checked.
- Subject incidence of TEAEs leading to prolongation of infusion time (>2.5 hours) by MedDRA SOC and PT.

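### The SAP's 2.5-hour cut-off for adverse-event-driven infusion prolongation has no stated basis and, on the standard 60 (±10) minute infusion, leaves half-rate slowing out of the prolongation summaries

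*SAP*

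**What the plan says.** SAP 9.2.2 lists, among the rows of the overall summary, "TEAE leading to prolongation of infusion time (>2.5 hours"). SAP 9.2.6 then plans "Subject incidence of TEAEs leading to prolongation of infusion time (>2.5 hours) by MedDRA SOC and PT". In that section the interruption, reduction and held tables are each tied to an Action Taken entry on the eCRF. The prolongation table has no stated data source, only the time limit.

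SAP 9.2 separately plans a by-subject listing of adverse events resulting in any dose change. It names prolongation as one kind of change and sets no time limit.

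Protocol 5.3 gives the infusion "at the infusion duration established in Study NEOD001-001 or over 60 (± 10) minutes", and adds: "The length of the infusion may be extended over a longer period of time as clinically indicated". For a Grade 2 infusion-related event, Protocol 5.4.2 says that "if it is appropriate to restart the infusion, it should be done at 50% of the original rate". Its example for a 60-minute infusion is the 250 mL bag over at least 90 minutes. After a Grade 3 event, if dosing continues, both the dose and the infusion rate are halved at the next administration.

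SAP 9.1 refers to "at least 50 minutes which is the lower limit of the protocol specified time". SAP 4.3, where one infusion time is missing and vital-sign times are unavailable, assumes 2 hours at Month 1 Day 1 and 1 hour at every other visit.

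**The concern.** Long-term safety and tolerability is the primary objective, and slowing the infusion is one of the protocol's tools for managing infusion reactions. The prolongation row should show how often that was needed. A fixed limit of 150 minutes is 2.5 times the 60-minute infusion (150/60 = 2.5), whereas the slowing that the protocol specifies is a doubling of time. A row that reads zero would suggest that no subject needed a longer infusion, when it may mean only that none passed 150 minutes.

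The limit is also uneven across subjects. The same relative slowing is counted for a subject with a long established infusion and not for one on the standard infusion. The table and the SAP 9.2 listing could then disagree, with prolongations in the listing and none in the table.

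**Working it through.** **Inputs**
- Cut-off: more than 2.5 hours = 2.5 × 60 = 150 minutes (SAP 9.2.2, 9.2.6). I read this as total infusion time. If it means added time, fewer events are counted.
- Infusion duration: the parent-study duration (value not given), or 60 (±10) = 50 to 70 minutes (Protocol 5.3).
- Slowing: 50% of the original rate (Protocol 5.4.2).

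**The plan's own figure.** The 2.5 hours cannot be reproduced. No derivation is given, and neither document uses it elsewhere.

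**Full volume at half rate.** Time = 2 × original time T.

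| T (min) | 2T (min) | Above 150? |
|---|---|---|
| 50 | 100 | no |
| 60 | 120 | no |
| 70 | 140 | no |
| 75 | 150 | no (break-even, 150/2) |
| 90 (assumed) | 180 | yes |
| 120 (assumed) | 240 | yes |

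The last two rows are an assumed range for the parent-study duration. The 120 minutes is borrowed from the SAP 4.3 imputation at Month 1 Day 1 and is not evidence of what was established.

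**Restart partway through.** If a fraction f was given before the stop, running time = fT + 2(1 − f)T. For T = 60 and f = 0.5 this is 30 + 60 = 90 minutes. If the pause counts as infusion time, it must exceed 150 − 90 = 60 minutes to pass the cut-off. For T = 70 and f = 0.25, running time is 17.5 + 105 = 122.5 minutes, and a pause above 27.5 minutes would do. The SAP does not say whether pauses count.

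**Half dose and half rate after a Grade 3 event.** If the rate is in mg per minute, time is 0.5T/0.5 = T, so 50 to 70 minutes. If it is in mL per minute on a 250 mL bag, time is 2T, so 100 to 140 minutes. Neither passes 150.

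**The protocol's example.** 250 mL over 60 minutes is 4.17 mL/min. Half of that is 2.08 mL/min, which takes 120 minutes. Over 90 minutes the rate is 2.78 mL/min, which is 60/90 = 67% of the original. The stated 50% and the 90-minute example do not agree.

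**The case against.** A reader might infer that every infusion in this study lasts 60 (±10) minutes, that half-rate slowing can never take more than 140 minutes, and that the prolongation row is therefore bound to be zero. The documents do not support this.
- Protocol 5.3 offers the parent-study duration as an alternative. All subjects had at least 9 months of treatment in that study, so it could apply to any of them.
- The 90 minutes in Protocol 5.4.2 is a minimum. Rates of later infusions after a Grade 2 event are agreed with the Medical Monitor, extension has no upper limit, and pauses may add time.

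Nor does missing from this row mean missing from the report. A Grade 2 half-rate restart follows a stop, so it may be counted under infusion interruption. A Grade 3 case that continues has its dose halved, so it may be counted under dose reduction. Both may be recorded as infusion-associated TEAEs (SAP 9.2.2, 9.2.9), and the SAP 9.2 listing can show prolongation of any length.

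Events are also likely to be few. Protocol 1.3.2 reports 9 infusion-site reactions in 6 of 69 parent-study subjects over 994 infusions. Seven were Grade 1, leaving 9 − 7 = 2 others. The analysis is descriptive, and SAP 11 records that the program was discontinued.

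All of this stands and limits the size of the point. It does not supply a reason for 2.5 hours, and it does not remove the mismatch between the tables and the listing. The other rows show that a reaction occurred or a dose was cut, not that infusion time was lengthened. With so few events, leaving out one or two can turn the row into zero.

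**Conclusion.** The point holds for subjects on the standard 60 (±10) minute infusion. A TEAE leading only to half-rate slowing (100 to 140 minutes) is left out of the SAP 9.2.2 row and the SAP 9.2.6 table unless pauses or further extension carry the time past 150 minutes. Where the parent-study duration exceeds 75 minutes, the same slowing over the full volume is counted. How many subjects fall on each side cannot be determined from the documents.

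The practical loss is mainly later infusions slowed without a stop or a dose reduction, together with a tolerability row that may read near zero for a reason of definition. No inferential result is affected. The conclusion assumes that 2.5 hours means total infusion time and that half rate applies to the full volume.

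Separately, the 50% rate and the 90-minute example in Protocol 5.4.2 contradict each other and must be reconciled. This review takes no position on which is right.

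**What to change.** In SAP 9.2.2 and 9.2.6, replace the 2.5-hour limit with prolongation relative to the subject's own reference infusion time. For example: recorded start-to-stop time more than 10 minutes longer than the subject's last infusion before the adverse event, or than the planned duration where that is recorded. The 10 minutes matches the protocol's own tolerance.
- Use the last infusion as the default reference. Nothing in the documents shows that the extension-study eCRF holds the parent-study duration, and Protocol 5.5 mentions only date, time and whether the infusion was completed.
- Use recorded times, not those imputed under SAP 4.3.
- Identify the adverse events by the same data field that feeds the any-dose-change listing, and name that field. SAP 9.2.6 cites no Action Taken entry for prolongation.
- State whether pauses count as infusion time.
- Keep more than 2.5 hours as a sub-row, with its rationale.

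The cost is a change of wording in two places and one extra derivation from infusion times. The reported count may rise. The Protocol 5.4.2 rate and its example should be reconciled by the sponsor as a separate matter.

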9.2.3. Treatment-Emergent Adverse Events

The crude and cumulative incidences of TEAEs will be summarized. The following summaries will be presented:

- Subject incidence of TEAEs by MedDRA SOC and PT
- Subject incidence of TEAEs by MedDRA SOC and PT occurring in $\geq 5\%$ of subjects

9.2.4. Severity of Adverse Events

The crude and cumulative incidences of TEAEs by maximum severity will be summarized. At each level of subject summarization, a subject is classified according to the highest severity if the subject reported 1 or more events. AEs with missing severity (CTCAE grade) will be considered Grade 3 (severe) for these summaries. The following summaries will be presented:

- Subject incidence of TEAEs by MedDRA SOC, PT, and highest severity (CTCAE grade)
- Subject incidence of CTCAE Grade 3 or higher TEAEs by MedDRA SOC and PT.

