9.2.1.2. Cumulative Incidence Rates

The cumulative incidence rate is the probability that a particular AE occurs by a specified time. To compute the cumulative rate using the life table method, exposure time intervals from the first NEOD001 dose of the original parent study (NEOD001-001) (i.e., ≤1 month, >1 month to ≤3 months, >3 month to ≤6 months, >6 months to ≤1 year, >1 to ≤1.5 years, >1.5 to ≤2 years, >2 to ≤3 years, ..., and > maximum years) are specified, and the number of subjects at risk of experiencing an AE in each time interval is determined by taking the average number of subjects at risk at the start and end of each time interval. As subjects leave the study over time, the number of subjects at risk of experiencing the AE in each time interval decreases. The cumulative incidence rate over each time intervals is as follows:

$$1 - \{[1 - P(t_1)][1 - P(t_2)] \dots [1 - P(t_k)]\}$$

where $P(t_i)$ is the number of subjects with the AE divided by the number of subjects at risk in time interval t_i and where i ranges from 1 to k .

To illustrate the difference between crude and cumulative incidence rates and how these are computed, an example is provided (O'Neill, 1988). Suppose that 3000 subjects are initially exposed to a drug and followed for up to 1 year with varying durations of exposure (see Table 7). Assume further that 30 subjects experience SAEs, most of which occur later in the study as duration of exposure increases. The crude rate is $30/3000 = 0.01$ and the 12-month cumulative rate is 0.055. When AEs occur later in time as fewer subjects are at risk due to discontinuations or tolerability, the crude rate underestimates the longer-term risk and overestimates the shorter-term risk.

Using the example in Table 7, the number of subjects at the start of a time interval is the number of subjects at the start of the previous time interval minus the number of subjects lost to follow-up or who dropped out minus the number of subjects with SAEs. For instance, the number of subjects at the start of the 3rd time interval is equal to

$$[1800 - 399 - 1] = 1400$$

The proportion of subjects with SAEs at each time interval $P(t_i)$ is computed by dividing the number of subjects with SAEs by the number of subjects at risk in the time interval. For example, the number of subjects at risk for the 2nd time interval is as follows:

$$\frac{[1800 + (1800 - 399)]}{2} = 1600.5$$

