9.2.5. Relationship to Study Drug as Assessed by Investigator

The crude and cumulative incidences of TEAEs by strongest relationship to study drug (Related/Not Related) will be summarized. At each level of subject summarization, a subject is classified according to the closest relationship to study drug if the subject reported 1 or more events. AEs with a missing relationship will be considered related for this summary. The following summaries will be presented:

- Subject incidence of related TEAEs by MedDRA SOC and PT
- Subject incidence of related CTCAE Grade 3 or higher TEAEs by MedDRA SOC and PT

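### Cumulative AE incidence by highest CTCAE grade (SAP 9.2.4) lets later events remove earlier lower-grade events, so early rates in those rows can only stay the same or fall as follow-up lengthens

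*SAP*

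**What the plan says.** SAP 9.2.4 plans crude and cumulative summaries together: "The crude and cumulative incidences of TEAEs by maximum severity will be summarized". The rule for placing a subject is that "a subject is classified according to the highest severity if the subject reported 1 or more events". The first output listed is "Subject incidence of TEAEs by MedDRA SOC, PT, and highest severity (CTCAE grade"), so rows for the lower grades are planned output. For incomplete records, "AEs with missing severity (CTCAE grade) will be considered Grade 3 (severe) for these summaries".

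SAP 9.2.1.2 gives the meaning of the cumulative figure: "The cumulative incidence rate is the probability that a particular AE occurs by a specified time". It uses a life table with intervals counted from the first parent-study dose, computed separately for each SOC and each PT within SOC.

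SAP 9.2.5 is built the same way. Its lead sentence reads "The crude and cumulative incidences of TEAEs by strongest relationship to study drug (Related/Not Related) will be summarized", and its rule is that "a subject is classified according to the closest relationship to study drug if the subject reported 1 or more events". Its listed outputs, however, cover related TEAEs only: "Subject incidence of related TEAEs by MedDRA SOC and PT", and the same for related events of Grade 3 or higher.

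The SAP does not limit the highest grade to events up to the time point being estimated. It also does not say which onset date places a subject in an interval.

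**The concern.** A probability of an event by month 3 cannot depend on month 20. Under the 9.2.4 rule it does. A subject with a Grade 1 event in month 2 and a Grade 3 event of the same PT in month 20 is a Grade 3 subject, so the month-2 event is missing from the Grade 1 row at every time point. Later events can take subjects out of a lower-grade row but never put them in, so the direction is known: the early rate stays the same or falls as follow-up lengthens.

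Long-term safety is the primary objective. SAP 9.2.1.2 introduces the life table because crude rates misstate shorter- and longer-term risk. In the lower-grade rows, the 9.2.4 rule brings a distortion over time back in. Two data cut-offs of the same study could give different 3-month rates although nothing in the first 3 months had changed.

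**Working it through.** **1. The plan's own figure.** SAP Table 7 uses: at risk = number entering − (number lost)/2; P(t_i) = events / at risk; cumulative rate = 1 − Π[1 − P(t_i)]. For the second interval, 1800 − 399/2 = 1600.5 and 1/1600.5 = 0.0006. All 12 rows reproduce to four decimals. They end at 0.0550, and the crude rate is 30/3000 = 0.01. The life-table method is sound; the question is what is counted as an event.

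**2. The mechanism by hand (invented counts).** Take 70 subjects, about the planned number. Suppose 21 have a Grade 1 event in month 1, and 9 of these have a Grade 3 event in the same SOC at month 30.
- Cut-off at 24 months: the month-1 rate in the Grade 1 row is 21/70 = 30.0%.
- Cut-off at 36 months: it is (21 − 9)/70 = 12/70 = 17.1%.

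**3. Size in closed form.** Protocol 1.3.2 lists common TEAEs in the parent study but gives no rates by grade and time, so the inputs are assumptions:
- p = 30%, the true 3-month risk of a Grade 1-2 event;
- h = 0.5%, 1% or 2% per month, the hazard of a later Grade 3 or higher event at the same SOC or PT level, independent of the early event;
- T = data cut-off in months from the first parent-study dose. At least 9 months in the parent study plus up to 36 months of OLE treatment means that T = 36 is within the planned span.

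The 3-month rate shown in the highest-grade row is p × exp[−h(T − 3)]. The exponent starts at month 3, so the result contains only the effect of later events. For h = 1% and T = 36: 0.30 × exp(−0.33) = 0.216.

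| h per month | T = 12 | T = 24 | T = 36 | T = 48 |
|---|---|---|---|---|
| 0.5% | 0.287 | 0.270 | 0.254 | 0.240 |
| 1% | 0.274 | 0.243 | 0.216 | 0.191 |
| 2% | 0.251 | 0.197 | 0.155 | 0.122 |

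**4. Simulation with the SAP's intervals.** Each setting used 69 subjects, 1,000 replicates, 1% dropout per month and interval limits at 1, 3, 6, 12, 18, 24, 36 and 48 months. The Grade 1-2 hazard was 0.12 per month, so 1 − exp(−0.36) = 0.302 by month 3. Subjects reclassified upward stayed in the lower-grade risk set without an event. The 3-month rates in the highest-grade row were:

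| h per month | T = 6 | T = 12 | T = 24 | T = 36 | T = 48 |
|---|---|---|---|---|---|
| 0.5% | 0.294 | 0.287 | 0.271 | 0.261 | 0.250 |
| 1% | 0.286 | 0.269 | 0.243 | 0.223 | 0.210 |
| 2% | 0.270 | 0.240 | 0.197 | 0.166 | 0.146 |

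Dropout shortens follow-up, so at the longer cut-offs the fall is somewhat smaller than in the closed form. When each event counts at its own onset, the 3-month rate stays at 0.300 to 0.306 for every cut-off. The 3-month Grade 3 or higher rate, timed at its first qualifying event, is also stable (about 0.015, 0.03 and 0.06).

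**5. How demanding the assumptions are.** By 36 months these hazards imply that 1 − exp(−36h) = 16%, 30% or 51% of subjects have a Grade 3 or higher event at that level. That is high for one PT. If only 2% to 5% later had such an event (also an assumption), 30% would become 0.30 × 0.98 = 29.4% to 0.30 × 0.95 = 28.5%. Among 69 subjects that is a change of 0.4 to 1.0 subject.

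**The case against.** The strongest reply is that SAP 9.2.4 is silent rather than wrong. It does not state that the maximum runs over all follow-up in the cumulative table, and a maximum to date would fit the definition in 9.2.1.2. But no section states that reading. Under it a subject would move between rows over time, and the product formula, which cannot decrease, has no step for that. The rule as printed gives one class per subject.

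Three further replies stand in part or in full:

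- **The early events are still reported.** SAP 9.2.3 plans crude and cumulative incidence of any TEAE by SOC and PT, and a month-2 Grade 1 event stays there whatever follows. A reader might infer that early risk is lost from the report. It is not; only its placement by grade is distorted.
- **The not-related half is thin.** A reader might infer that 9.2.5 has the same fault to the same degree. A Not Related row would, but only the lead sentence there mentions one. The listed outputs are for related events, the top class, from which later events cannot remove anyone.
- **The consequence is limited.** The study has no inferential safety comparison (SAP 9), all AEs are listed by subject, and no decision in the documents is shown to rest on the lower-grade cumulative rows. Discontinuation of the programme (SAP 11) may also have shortened follow-up.

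**Conclusion.** The point holds for the cumulative version of the table by SOC, PT and highest CTCAE grade in SAP 9.2.4. Rows below the top grade do not estimate the probability that 9.2.1.2 defines, and their early values can only stay the same or fall as follow-up lengthens.

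The direction follows from the rule; the size does not. The fall from 30% to about 25% to 16% at 36 months rests on the assumed risk, hazards and independence. It describes a level where worse events are fairly common, which is more likely for an SOC than for a single PT. A large distortion in single-PT rows is not supported by the documents.

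It would also go too far to call all the severity and relationship tables biased. The any-TEAE, Grade 3 or higher and related tables are sound if each is timed at its first qualifying event. The SAP does not name that date. Timing them instead at the subject's first AE of any grade or relationship would inflate their early rates. No hypothesis test or sample size is affected.

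**What to change.** In SAP 9.2.4, keep the highest-grade classification for crude tables only. For cumulative incidence, use time to first TEAE of Grade ≥1, ≥2, ≥3 and ≥4 by SOC and PT, and state that each is timed at the onset of its own first qualifying event. In SAP 9.2.5, limit cumulative incidence to time to first related TEAE, timed in the same way.

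Any-grade (9.2.3), Grade ≥3 (9.2.4) and related (9.2.5) tables are already planned, so only the Grade ≥2 and ≥4 thresholds are new. The cost is SAP wording and a changed event definition in the programs, with no new data.
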